Study Protocol

Home-based Resistance Training to Patients With Type 2 Diabetes

NCT04755660

Document Date: 2021.01.18

Study Protocol

Purpose: The purpose of the study is to explore the efficacy of a theory-based resistance exercise intervention and a resistance band exercise training on the level of physical activity, muscle strength body composition, exercise self-efficacy, and exercise adherence in adults with type 2 diabetes.

Methods: The study is a three-arm parallel randomized clinical trial. Participants were recruited from metabolism outpatient clinics. A total of 90 adults with type 2 diabetes were recruited and randomly assigned to the theory-based resistance exercise group, the resistance band exercise training group, or the control group. All groups underwent a 12-week intervention program. The theory-based resistance exercise group received a 12-week motivational interviewing and self-efficacy based resistance exercise training. The resistance band exercise group received a 12-week resistance band exercise training. All participants were introduced to exercise three times a week and at least thirty minutes a day on alterative day. The control group received a brief exercise instruction. Data were collected at the pretest, 6th week, and 12th week on handgrip strength, 6 meters walking speed (6 MWS), 30 seconds sit to stand (30' STS), self-reported physical activity, and exercise self-efficacy. The participants were asked to keep daily exercise dialog as well.

[name]
[contact]

新光醫療財團法人
新光吳火獅紀念醫院

SHIN KONG WU HO SU MEMORIAL HOSPITAL

E-mail : [contact]
[contact]

人體試驗委員會
同意人體研究證明書

計畫名稱：比較行為介入與居家阻力運動訓練對改善第二型糖尿病病人身體活動量與肌力之
成效：隨機分派臨床研究

計畫書編號/本會審查編號：20201202R

計畫書版本/日期：Version 3, 2021-03-03

計畫總主持人：[name]

計畫主持人所屬機構：新光醫療財團法人新光吳火獅紀念醫院台北護理健康大學

受試者同意書版本/日期：Version 2, 2020-12-28

通過會期：No.3/2021-3-11

核准效期：2021-01-18 至 2022-01-17

計畫追蹤頻率：每 12 個月一次。

期中報告繳交期限：2022-01-17(建議於前 6 週完成繳交以利期限前審畢)

結案報告繳交期限：2022-03-17(核准效期迄日後 2 個月內繳交)

其他：個案檢查資料登錄查核表 Version 2, 2020-12-28、運動日誌 Version 2, 2020-12-28、

個案招募篩檢表 Version 1, 2020-11-30、個案基本資料表 Version 1, 2020-11-30、

運動自我效能量表 Version 1, 2020-11-30、老人身體活動量表 Version 1, 2020-11-30、

招募海報 Version 1, 2020-11-30

Institutional Review Board
Approval of Human Study

Protocol Title : Comparing the Efficacy of a Behavioral Intervention and a Home-based Resistance Training of Physical Activity and Muscle Strength in Patients with Type 2 Diabetes:
A Randomized Clinical Trial

Protocol No./IRB No. : 20201202R

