**NCT04755660**

**Document Date: 2021.01.18**

## Statistical Analysis Plan

The results of this study were archived and analyzed with SPSS 22 package software, and the statistical significance level of Type I error was set at  $P<0.05$ , and the power was set at 80%. Every time the case data collection is completed, the data input and file building are completed on the same day. Before the data is analyzed, the distribution of each variable will be checked for outliers and missing values. Those who quit halfway are also encouraged to fill out the post-test questionnaire.

The basic attributes and disease characteristics of the research objects are presented in the form of frequency distribution, percentage, average value, and standard deviation. One-way ANOVA or Chi-Square test was used to examine the homogeneity of demographics, disease characteristics and pretest data of research variables among the groups. One-way ANOVA was used to examine the differences in blood glucose, body composition, muscle strength, physical activity, and self-efficacy scores between different groups between the sixth week and the 12th week. The t-test was used to examine the difference in exercise compliance between the behavioral intervention group and the home resistance training group. The generalized estimating equation (GEE) was used to analyze the differences in blood glucose, body composition, muscle strength, physical activity, and self-efficacy over time among different groups.

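### Does the plan need to name the one test, visit and arm comparison that gives the muscle strength result?

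*Protocol*

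**What the plan says.** The Methods paragraph of the protocol lists three physical tests, "handgrip strength, 6 meters walking speed (6 MWS), 30 seconds sit to stand", with self-reported physical activity and exercise self-efficacy. All are measured at pretest, week 6 and week 12. Only handgrip carries the word strength. The ethics-approved title on the approval certificate ends "Home-based Resistance Training of Physical Activity and Muscle Strength in Patients with Type 2 Diabetes", so strength is one of its two outcomes. The Purpose paragraph opens "The purpose of the study is to explore the efficacy of a theory-based resistance exercise intervention".

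The second paragraph of the SAP treats muscle strength as one of five domains and analyses it twice. A one-way ANOVA covers "muscle strength, physical activity, and self-efficacy scores between different groups between the sixth week and the 12th week". The GEE is "used to analyze the differences in blood glucose, body composition, muscle strength, physical activity, and self-efficacy over time among different groups". None of the three physical tests appears by name, and no model term, deciding visit or pair of arms is given. The only two-arm comparison the SAP describes is the t-test on exercise compliance. The first paragraph says "the statistical significance level of Type I error was set at" P<0.05 and "the power was set at 80" per cent, tied to no outcome.

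**The concern.** An outcome in the trial's title should be traceable from measurement to test, and here it is not.

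- The strength label could mean handgrip alone, handgrip with sit-to-stand, or all three physical tests.
- On the first two readings, walking speed falls under no analysis.
- Even for handgrip alone, there are an ANOVA and a GEE, two follow-up visits and three pairs of arms.
- The ANOVA sentence could mean a test at each of weeks 6 and 12, or a single test of the change between them. The second reading leaves out the pretest.

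These analyses can disagree. If the choice among them waited until the results were known, strength improved and strength did not improve could both be reported as following the plan. A P value below 0.05 would then no longer carry its usual meaning for this outcome.

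**Working it through.** **The plan's own figure.** The 80% power cannot be reproduced, because no effect size, SD, outcome or contrast goes with it. It can only be turned round. The protocol states "A total of 90 adults with type 2 diabetes were recruited and randomly assigned" to three arms; an equal split of 90/3 = 30 per arm, no dropout and a two-sided 5% level are assumed. Power of 80% then corresponds to f of about 0.33 for the three-group ANOVA, or a standardized difference of about 0.74 for one pair of arms. Neither figure shows which outcome was meant.

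**Error rates if any positive test could carry the claim.** The rule is hypothetical. For m independent tests, the chance of at least one false rejection is 1 - 0.95^m: 9.75% for m = 2, 14.3% for m = 3 and 26.5% for m = 6. The real tests are correlated, so simulation under no effect is needed. It uses 3 x 30 participants, between-test correlation 0.3 to 0.7 and within-person correlation 0.5 to 0.9, all assumed. The GEE is represented by a 4-df multivariate test of changes from pretest, since the SAP names no GEE term.

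The harm in question is a false statement that strength improved. An omnibus rejection is not that: it also occurs when control does best or when only the two exercise arms differ. The last column therefore also requires an exercise arm to be significantly above control.

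| What could carry the claim | Any omnibus rejection | With an exercise arm above control |
|---|---|---|
| One test, one visit | 5% | 2.1% |
| Handgrip or sit-to-stand, one visit | 8.6-9.5% | 3.7-3.9% |
| One test; ANOVA at week 6, ANOVA at week 12, or GEE | 11.7-13.0% | 5.0-6.0% |
| One test; ANOVA of week-6-to-12 change, or GEE | 7.6-7.9% | 3.5-4.1% |
| Both tests; any of the three analyses | 19.2-23.8% | 8.4-10.6% |
| Both tests; ANOVA of change, or GEE | 12.8-14.8% | 6.3-7.6% |

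Only the two rows with both tests and more than one analysis lie clearly above 5% in the last column.

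**What naming one result would cost.** Take 30 v 30 and a true difference of 0.736 SD of change on both tests. A single named test has 80% power; an either-test rule has 88.7% to 93.5% (between-test correlation 0.7 to 0.3). If only the unnamed test truly changes, the named one supports the claim with probability 2.5%.

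**The two readings of the ANOVA sentence.** The sentence before it uses one-way ANOVA to compare the groups on pretest data. Carrying the same test on to weeks 6 and 12 is the natural sequel, and the sentence speaks of scores, not changes. Change over time is what the GEE sentence then covers. The per-visit reading therefore fits the paragraph better, though the words do not exclude the other.

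**The case for a change.** The strongest case for a change is that the SAP sets a 5% level and 80% power, the aim is efficacy, and strength is in the title. An exploratory aim does not tell a reader which number is the strength result. Assuming that handgrip is meant does not settle it, because several analyses remain. Relative to a single directional test at 2.1%, the inflation is real: 8.4/2.1 = 4.0 to 10.6/2.1 = 5.0 times with both tests and all three analyses. The repair would be a few lines of wording.

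Unadjusted pairwise comparisons would look worse. Two tests, two visits and three pairs make 12 comparisons, with a simulated chance of at least one false positive of 26-40%; counting walking speed makes 18, and 34-54% (correlations assumed from zero up to 0.7 between tests and 0.9 between visits). But those rates count differences in either direction among all pairs, and the SAP plans no pairwise tests of strength.

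What stands is that the mapping from tests to domains is unstated and that the ANOVA wording is loose. The further step, that the plan licenses picking a winner, does not stand. The SAP lists the ANOVA and the GEE as analyses to be done, not as alternatives, so discordant results would be reported as discordant. For walking speed, the accurate statement is that the SAP does not name it. It may have been meant to fall under strength, on the reading that takes all three physical tests together, or under physical activity.

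**Conclusion.** No change to the plan follows. This is a gap that an analyst fills sensibly: analyse handgrip, sit-to-stand and walking speed each by the ANOVAs and the GEE, label each by its own name, and report them all whatever they show. Done that way, the results are sound for an exploratory study.

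Naming one test, visit and contrast in advance is an option, but not a clearly better method. The documents do not single out handgrip, week 12 or theory-based versus control, and the approved title compares the two interventions with each other. The choice would also give up power if both tests respond, and would lose the strength claim if only the other one does.

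The chance of a false claim of improvement, about 4%, 5-6% and 8-11% in the three main scenarios against about 2% for one test, rests on a claim rule that the documents do not state. It also rests on 30 per arm, no dropout, assumed correlations and a stand-in for the GEE. Finally, the ethics certificate cites a Version 3 protocol dated 2021-03-03, later than the supplied document of 2021-01-18, and an examination-data checklist. Neither is available here, and either may already define the measure.

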**NCT04755660**

**Document Date: 2021.01.18**

## Statistical Analysis Plan

The results of this study were archived and analyzed with SPSS 22 package software, and the statistical significance level of Type I error was set at  $P<0.05$ , and the power was set at 80%. Every time the case data collection is completed, the data input and file building are completed on the same day. Before the data is analyzed, the distribution of each variable will be checked for outliers and missing values. Those who quit halfway are also encouraged to fill out the post-test questionnaire.

The basic attributes and disease characteristics of the research objects are presented in the form of frequency distribution, percentage, average value, and standard deviation. One-way ANOVA or Chi-Square test was used to examine the homogeneity of demographics, disease characteristics and pretest data of research variables among the groups. One-way ANOVA was used to examine the differences in blood glucose, body composition, muscle strength, physical activity, and self-efficacy scores between different groups between the sixth week and the 12th week. The t-test was used to examine the difference in exercise compliance between the behavioral intervention group and the home resistance training group. The generalized estimating equation (GEE) was used to analyze the differences in blood glucose, body composition, muscle strength, physical activity, and self-efficacy over time among different groups.

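### The SAP asks people who quit only for the post-test questionnaire, so the per-visit ANOVAs of strength, body composition and glucose are unadjusted available-case comparisons, and the GEE's missing-data assumption is unstated

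*SAP*

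**What the plan says.** The SAP's first paragraph has two sentences that bear on incomplete follow-up. One concerns data checking: "Before the data is analyzed, the distribution of each variable will be checked for outliers and missing values". The other concerns people who stop: "Those who quit halfway are also encouraged to fill out the post-test questionnaire". In the text available, neither document gives a method for missing values, a missingness assumption or a sensitivity analysis.

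The SAP's second paragraph then plans two analyses of the same outcomes:

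- A one-way ANOVA: "One-way ANOVA was used to examine the differences in blood glucose, body composition, muscle strength, physical activity, and self-efficacy scores between different groups". The sentence goes on to name the sixth and twelfth weeks. I read it as one comparison at each visit. If it instead means the change between those weeks, it still needs the week-12 value.
- A longitudinal model: "The generalized estimating equation (GEE) was used to analyze the differences in blood glucose, body composition, muscle strength, physical activity, and self-efficacy over time". No working correlation or weighting is given.

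The protocol's Methods paragraph lists the visits and the physical tests: "Data were collected at the pretest, 6th week, and 12th week on handgrip strength, 6 meters walking speed (6 MWS), 30 seconds sit to stand". Walking speed and sit-to-stand are not named in the SAP and may be meant to fall under muscle strength. Body composition and blood glucose are named in the SAP analyses but not in the protocol's list of data collected.

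**The concern.** A questionnaire can supply self-reported activity and self-efficacy. It cannot supply handgrip, walking speed, sit-to-stand, body composition or blood glucose. Staff following the SAP literally would seek self-report from someone who has stopped and would have no instruction to seek the rest. The measured outcomes would then rest on fewer participants, and different ones, than the self-report outcomes.

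Muscle strength is in the ethics-approved title and body composition is in the stated purpose, so the gap falls on central outcomes. The arms also differ in burden: two 12-week training programmes against brief exercise instruction. Quitting that differs by arm and is related to physical ability is therefore plausible, although the documents give no data on it. Where that happens, the people measured at week 12 are no longer the groups that randomisation produced. An unadjusted comparison at that visit uses none of the earlier information that could help to correct for this.

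**Working it through.** **Inputs.** The protocol gives 90 randomised to three arms. The allocation ratio is not stated, so I assume 90 / 3 = 30 per arm. The SAP gives alpha 0.05 without sidedness; I assume two-sided. The documents give no quit rate, no difference between quitters and completers, and no effect size. There is therefore no planned dropout figure to reproduce, and everything below is a range under assumptions.

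**Step 1: bias in an available-case contrast.** Let p be the proportion lost in an arm and g the gap, in SD, between the means of completers and quitters. The full-arm mean is (1 − p) × completer mean + p × quitter mean. Hence completer mean − full mean = p × g, and the bias in the contrast of arm 1 with arm 0 is

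p1 × g1 − p0 × g0,

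which becomes (p1 − p0) × g when the gap is the same in both arms.

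**Step 2: effect on the test.** With no true effect, a two-sided 5% t-test of two arms has noncentrality bias / √(1/n1 + 1/n0). With 20% lost, 30 × 0.80 = 24 per arm and the denominator is √(2/24) = 0.289.

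| Quitting (assumed) | Gap g (assumed) | Bias (SD) | Noncentrality, 24 v 24 | Rejection, 24 v 24 | Rejection, arm sizes implied by the quit rates |
|---|---|---|---|---|---|
| 20% v 10% | 0.5 SD | 0.10 × 0.5 = 0.05 | 0.173 | 5.3% | 5.4% (24 v 27) |
| 20% v 10% | 1 SD | 0.10 × 1 = 0.10 | 0.346 | 6.3% | 6.4% (24 v 27) |
| 30% v 10% | 0.5 SD | 0.20 × 0.5 = 0.10 | 0.346 | 6.3% | 6.3% (21 v 27) |
| 30% v 10% | 1 SD | 0.20 × 1 = 0.20 | 0.693 | 10.4% | 10.3% (21 v 27) |
| equal | equal | 0 | 0 | 5.0% | 5.0% |

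These are pairwise figures and illustrate the three-arm ANOVA rather than reproduce it.

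**Step 3: equal quit rates are not enough.** The gaps must be equal too. Take a true effect of zero, correlation 0.6 between visits and 20% lost before week 12 in each arm. Loss is random in one arm. In the other it depends on the week-6 value plus noise of SD 0.7. That selection score has SD √(1 + 0.49) = 1.22, and a standard normal variable above its 20th percentile has mean 0.35. The week-12 completer mean in that arm therefore shifts by (0.6 / 1.22) × 0.35 = 0.17 SD. This is the Step 1 formula with p = 0.20 in both arms and gaps of 0.86 and 0: 0.20 × 0.86 − 0.20 × 0 = 0.17.

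**Step 4: the ANOVA and the GEE compared.** A simulation of that setting (3,000 per arm, six runs) gave these mean biases in the week-12 contrast:

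- Available cases only, which is what the ANOVA uses: 0.17 SD.
- GEE with independence working correlation: 0.17 SD.
- GEE with exchangeable working correlation: 0.005 SD.

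The exchangeable model borrows from the pretest and week-6 values of those who left. It does well here partly because exchangeable was the true structure and loss depended only on an observed value. The result shows that the unstated choice matters, not that any one choice is safe.

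**The case against.** The strongest reply is that the SAP is silent rather than restrictive. Its sentence on quitters adds an encouragement and withholds nothing, and the protocol schedules week-6 and week-12 assessments with no exception for people who stop. This stands. A reader might infer that quitters are followed by questionnaire alone, but the text does not say so. The defect is a missing instruction.

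Four other stronger readings are tempting and should not be adopted.

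- *That the GEE is also a completer analysis.* It is not: it keeps every visit observed before someone leaves. Its weakness is the unstated working correlation and missingness assumption.
- *That participants may not be analysed as randomised.* The protocol defines the groups by random assignment, and the SAP sets up no as-treated or per-protocol set and no exclusion for poor adherence. Analysis by assigned arm is the plain reading, and an explicit sentence is only a clarification.
- *That any bias favours the more demanding arms.* Nothing in the documents supports a direction.
- *That the trial loses a stated amount of power.* This would require the 90 to contain no dropout allowance, and the documents do not say whether it does.

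It is also fair to say that the mildest scenario is trivial (5.3% against 5%), and that reaching about 10% needs both 30% v 10% quitting and a 1 SD gap. This bears on size. It does not supply the missing instruction or the missing assumption.

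**Conclusion.** The concern holds in a limited form. The only stated follow-up of people who quit cannot yield the physical or laboratory outcomes. As written, the week-6 and week-12 ANOVAs of those outcomes are unadjusted available-case comparisons. The GEE is less exposed, to a degree that depends on choices the SAP does not state.

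Under quit-rate differences of 10 to 20 percentage points and completer–quitter gaps of 0.5 to 1 SD, all assumed, the bias is 0.05 to 0.20 SD and the false-positive rate about 5% to 10%. These figures further assume equal allocation, a two-sided test and the same gap in both arms compared. The bias is zero when quit rates and gaps are equal across arms. Its actual size and direction cannot be determined from the documents. The change is worth making because it is cheap and because measurements not taken from people who stop cannot be recovered later.

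**What to change.** 1. Replace the sentence on people who quit with: *Participants who stop the exercise programme but have not withdrawn consent are invited to the full scheduled week-6 and week-12 assessments: handgrip, 6 MWS, 30-second STS, body composition, blood glucose and questionnaires.*

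2. In place of the unadjusted per-visit ANOVAs, base the between-group comparison on one repeated-measures analysis in assigned arms that uses the pretest value and all observed visits. Either of these would serve:
   - a likelihood-based mixed model with the pretest included as an outcome, so that people who quit before week 6 are kept (a model with pretest only as a covariate would drop them); or
   - the planned GEE with a stated non-independence working correlation, chosen to reflect the expected correlation between visits, or with inverse-probability weights.

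   State the missingness assumption in either case.

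3. Report missing data by arm and by outcome.

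The first change matters most, because no model can fully correct for quitting that depends on values nobody measured. If follow-up has already ended, only the second and third can still be made.

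The cost is a few extra assessments at visits that already exist, which some people will decline, and slightly more analysis work. Using the pretest value should also improve precision.

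### The planned group comparisons at weeks 6 and 12 leave out the pretest, and no pretest-adjusted analysis is specified, which costs precision

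*SAP*

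**What the plan says.** The Protocol (Study Protocol, Methods) describes three parallel arms and 90 participants: "A total of 90 adults with type 2 diabetes were recruited and randomly assigned". Outcomes are measured three times: "Data were collected at the pretest, 6th week, and 12th week on handgrip strength", followed by walking speed, sit-to-stand, physical activity and exercise self-efficacy.

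The SAP (Statistical Analysis Plan, second paragraph) then does three things with the outcomes.

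- It tests baseline comparability: "One-way ANOVA or Chi-Square test was used to examine the homogeneity of demographics, disease characteristics and pretest data". This is the only place where the SAP names the pretest.
- It compares groups at follow-up: "One-way ANOVA was used to examine the differences in blood glucose, body composition, muscle strength, physical activity, and self-efficacy scores", with the timing given as "between different groups between the sixth week and the 12th week". No covariate is named.
- It plans a longitudinal model: "The generalized estimating equation (GEE) was used to analyze the differences in blood glucose, body composition, muscle strength", then physical activity, "and self-efficacy over time among different groups". It does not say whether the pretest is a response or a covariate, whether group-by-time is the treatment contrast, or which working correlation is used.

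The first paragraph of the SAP fixes the significance level at 0.05 and the power: "and the power was set at 80" per cent. No effect size, SD, correlation or allocation ratio is given. Nothing says whether the ANOVA or the GEE provides the conclusion.

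**The concern.** A person's pretest value usually predicts the follow-up value of the same outcome. A comparison that ignores it leaves that predictable variation in the error term. With about 30 per arm the loss can be large for outcomes that are stable within a person, and small for those that are not.

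The GEE does not clearly make up for this. The natural reading is a group-by-time model over pretest, week 6 and week 12. If that model is saturated and the data are complete, its treatment contrast is a difference in change from pretest. Such a contrast can be less precise than ignoring the pretest altogether. A longitudinal model with a common pretest mean across arms and a suitable correlation structure would come close to ANCOVA, but the SAP neither specifies nor excludes it. The ANOVA and the GEE can therefore disagree on the same outcome, with no rule for which one stands.

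**Working it through.** **The plan's own figure.** N = 90 cannot be reproduced, because no effect size, SD, correlation or dropout is given. Back-solving the noncentral F distribution for three groups (df 2 and 87, noncentrality N·f²) gives 80% power at f = 0.333. When one arm differs from the other two by d SD, f = d·√2/3, so this corresponds to d = 0.706.

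**Inputs.** From the documents: 90 participants, three arms, 5% level, 80% power. Assumed: 30 per arm, complete data, ANOVA on levels at one visit, means (0, 0, 0.5) in SD units, equal SD at pretest and follow-up, and r from 0.3 to 0.9.

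**Variance of each comparison relative to the ANOVA on levels.**

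- Levels: 1
- Change from pretest: 2(1 − r)
- ANCOVA: 1 − r²

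Change beats levels only if 2(1 − r) < 1, that is r > 0.5. ANCOVA relative to change is (1 − r²)/[2(1 − r)] = (1 + r)/2, which is below 1 for every r < 1. The precision loss against ANCOVA is therefore r² for levels and 1 − (1 + r)/2 for change.

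**Noncentrality.** The grand mean is 0.5/3 = 0.1667, so λ = 30 × (2 × 0.1667² + 0.3333²) = 5.0, divided by the variance factor. For ANCOVA at r = 0.7, λ = 5.0/0.51 = 9.80. Error df is 87 for levels and change, 86 for ANCOVA.

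| | r = 0.3 | r = 0.5 | r = 0.7 | r = 0.9 |
|---|---|---|---|---|
| Power, levels ANOVA | 48.9% | 48.9% | 48.9% | 48.9% |
| Power, change contrast | 36.4% | 48.9% | 72.0% | 99.5% |
| Power, ANCOVA | 52.9% | 61.6% | 79.3% | 99.7% |
| Precision loss v ANCOVA, levels | 9% | 25% | 49% | 81% |
| Precision loss v ANCOVA, change | 35% | 25% | 15% | 5% |
| Detectable difference at 80% power, levels (SD) | 0.71 | 0.71 | 0.71 | 0.71 |
| Detectable difference, change (SD) | 0.84 | 0.71 | 0.55 | 0.32 |
| Detectable difference, ANCOVA (SD) | 0.67 | 0.61 | 0.50 | 0.31 |
| n per arm for 80% power at 0.5 SD, levels | 59 | 59 | 59 | 59 |
| n per arm, change | 82 | 59 | 36 | 13 |
| n per arm, ANCOVA | 54 | 45 | 31 | 13 |

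A simulation of 40,000 trials per r agreed: levels 48.8–49.3%; ANCOVA 52.3%, 61.0%, 78.7%, 99.7%; change 36.1%, 48.5%, 72.0%, 99.6%.

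**Sensitivity.**

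- 25 analysed per arm: 42% unadjusted, against 45%, 53%, 71% and 99% with the covariate.
- 30 per arm with means (0, 0.25, 0.5): λ = 30 × (2 × 0.25²) = 3.75; 38% unadjusted, against 41%, 49%, 66% and 98%.

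**The case against.** The strongest reply is that the GEE covers every outcome domain and, on its natural reading, does use the pretest. Setting 49% beside 99.7% then overstates the loss, because for stable outcomes a change-type GEE already captures most of the gain. This is fair as far as it goes. Against the better of the two planned analyses at each r, ANCOVA gains about 4, 13 and 7 points at r = 0.3, 0.5 and 0.7, and under 1 point at 0.9. But r is not known in advance, the SAP does not say which analysis decides, and ANCOVA is ahead of both at every r shown.

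The break-even at r = 0.5 also belongs to a single-visit contrast. If the GEE averaged weeks 6 and 12, with the same correlation r between all pairs of visits and the same 0.5 SD effect at both, the change factor would be (1 + r)/2 + 1 − 2r = 1.5(1 − r). Break-even with a single-visit ANOVA moves to r = 1/3, and power is 47%, 62% and 84% at r = 0.3, 0.5 and 0.7. That stands, but adjusting the same averaged contrast gives a factor of (1 + r)/2 − r², which at r = 0.5 is 0.5 against 0.75 and gives 80% against 62%.

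Three further points are right but leave the concern intact.

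- The ANOVA timing phrase could mean change from week 6 to week 12. The 49% would not then apply, but the pretest would still be unused.
- The 0.5 SD effect is an assumption. At 0.71 SD the unadjusted test reaches 80%, so these figures do not show that the trial is underpowered.
- The Protocol's list of measurements by visit omits blood glucose and body composition. That their pretests exist is inferred from the SAP's homogeneity sentence.

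**Conclusion.** The concern holds. The ANOVA uses no pretest, and no analysis with the pretest as covariate is written down; the GEE is too loosely described to supply one. Randomisation keeps the unadjusted comparison unbiased and its type I error at 5%, so the cost is efficiency, together with two unranked analyses of the same outcomes.

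The size depends on r. Under the stated assumptions, the ANOVA gives up 9% of the attainable precision at r = 0.3 and 49% at r = 0.7. A change-type GEE gives up 35% and 15% at those values. For weakly correlated outcomes the benefit over the ANOVA is modest; for stable ones it can bring the difference detectable with 80% power from 0.71 SD to 0.50 SD or less. This should be fixed, because the gain comes from data the trial already plans to hold.

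**What to change.** Name one main analysis per outcome, with the pretest value of that outcome as a prespecified covariate. Either of these will do:

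- ANCOVA at week 6 and at week 12; or
- a GEE or mixed model with weeks 6 and 12 as responses and with pretest, group, visit and group-by-visit as terms.

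Report adjusted mean differences with 95% confidence intervals. State that the adjustment is made whatever the homogeneity tests show. Clarify whether the ANOVA compares levels at each visit or change between the two visits; the one-way ANOVAs may stay as secondary analyses. Confirm that pretests of blood glucose and body composition are collected.

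The cost is SAP wording and about one error degree of freedom per outcome. No new data are needed where the pretest is collected, and the models are available in SPSS.
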